4.4. Visit Windows

In general, data for assessments that are collected by scheduled visits will be mapped to visits that appear in the schedule of assessments per the protocol using the actual study day of assessment. Data mapped to scheduled visits will include all data collected up to the reporting cut-off date and may include withdrawal visits and unscheduled visits.

Visit windows will be continuous from the midpoint between two consecutive study visits and will be dependent on the schedule of assessments for each variable independently. The exception is the Week 16 analysis window, which has been extended to allow for potentially delayed visit due to COVID-19 pandemic. An example of the Vital Signs visit window is given in [Table 4-1](#). Visit windows for each variable will be constructed in the same manner.

Table 4-1: Visit Windows

Study Visit	Scheduled Day	Analysis Window
Baseline	1	≤ 1
Week 4	28	>1 to ≤ 56
Week 12	84	>56 to ≤ 98
Week 16	112	>98 to ≤ 154
Week 24	168	>154 to ≤ 210
Week 36	252	>210 to ≤ 294
Week 48	336	>294 to ≤ 378

4.5. Multiple Values

For summaries displayed by visit, multiple values for a given assessment within a time window will be handled as follows:

- **Efficacy:** The nearest non-missing value to the nominal timepoint will be assigned to the visit. If two values are equidistant from the nominal timepoint then the latest value will be selected.
- **Safety:** The first non-missing value to the nominal timepoint will be assigned to the visit.

For the PK and biomarker data, if the assay is believed to have failed for an assessment due to technical reasons, the sample will be re-run and the last/latest assessment date/time that is available will be used for the data analysis.

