A thorough QT study (PM1116628) was conducted with losmapimod at 7.5 mg BID or 20 mg daily or with placebo administered for 5 days. At the 20 mg dose of losmapimod, the upper bound of the 90% confidence interval (CI) of the $\Delta\Delta QT$ interval corrected for heart rate by Fridericia's formula (QTcF) (change from baseline in QTcF compared to that for placebo) exceeded the 10 msec threshold at the 24-hour postdose time point. For the 7.5 mg BID dose, the upper bound of the 90% CI of $\Delta\Delta QTcF$ exceeded the 10 msec threshold at multiple time points. No subjects experienced QTcF values >480 msec or QTcF changes from baseline ≥ 60 msec at any time in the study. Although the upper bound of the 90% CI exceeded the 10 msec regulatory threshold of concern in the primary PD analysis, GSK stated that there was no clinically relevant effect on the QT interval, as there was no clinically relevant concentration QTc effect using standard placebo/baseline subtracted measured QTc data. Additional information on the QTc interval and its behavior, as demonstrated in the large cohort of patients treated with losmapimod obtained from Study PM1116197, supported the lack of a QT effect. PK/PD modeling using the raw QTcF and plasma concentration data showed that at plasma losmapimod concentrations 4 times the exposure at the therapeutic dose (7.5 mg BID), ie, at exposures approximately 2-fold higher than 15 mg BID, the predicted upper bound of the 90% CI of $\Delta\Delta QTcF$ did not exceed 10 msec and the predicted median $\Delta\Delta QTcF$ was less than 5 msec. Further details are presented in the investigator's brochure (IB).

In summary, review of studies in healthy volunteers and patient populations did not identify differences in the type, frequency, or severity of AEs or SAEs between losmapimod and placebo. No definitive safety signals have been identified.

Further details regarding the nonclinical and clinical data are presented in the IB.

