9.5. Electrocardiogram

All subjects will have a standard 12-lead ECG performed during the study as clinically indicated. Electrocardiogram data for all subjects will also be presented in a listing.

Descriptive summaries will be provided for the ECG data including ventricular rate (bpm), PR interval (msec), QRS duration (msec), QT interval (msec), and QTcF interval (msec) by treatment group for subjects in the Safety Analysis Set. In addition, number and percentage of subjects with normal sinus rhythm will also be presented in a table. Observed results at each visit will be presented. Change from baseline to each post-dose assessment will also be presented.

The number and percentage of subjects with an overall evaluation of ‘Normal’, ‘Abnormal, Not Clinically Significant’, or ‘Abnormal, Clinically Significant’ will be presented for baseline, Week 4, Week 48, End of Treatment, and Safety Follow-up.

A categorical summary of QTcF values and change from baseline at each visit will be presented by number and percentage for the Safety Analysis Set. Categories for reporting absolute QTcF interval are defined as: >450 to 480 msec, >480 to 500 msec, and >500 msec. Change from baseline in QTc interval is classified as: >30 to 60 msec increase from baseline and >60 msec increase from baseline.

ECG data for all subjects will also be presented in a listing.

10. Pharmacokinetics

By-subject listing of pharmacokinetic blood sample and muscle sample collection times as well as derived sampling time deviations will be provided. Losmapimod plasma and muscle concentrations will be summarized using descriptive statistics (n, mean, standard deviation, minimum, median, maximum, coefficient of variation) by scheduled time point. Concentrations that are below the limit of quantitation (BLQ) will have a value of LLOQ value divided by 2 in the computation of descriptive statistics. Mean concentration-time data will be graphically presented. All data presentation will use the PK Analysis Set.

Predose samples that are missing will be assigned as missing.

Concentrations assigned a value of missing will be omitted from the calculation of descriptive statistics. A concentration value of zero will be included for the computation of arithmetic mean. If 50% or more of the values are BLQ at one scheduled time point, the arithmetic mean will be reported as BLQ.

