Table	14.3.1.4.1	Treatment-Emergent Adverse Events by Maximum Severity	Open-label losmapimod (Pre-COVID-19) Analysis Set	R	9.1.3	Safety		
Table	14.3.1.5	Treatment-Emergent Adverse Events Leading to Treatment Discontinuation by System Organ Class and Preferred Term	Safety Analysis Set	R	9.1.5	Safety		
Table	14.3.1.5.1	Treatment-Emergent Adverse Events Leading to Treatment Discontinuation by System Organ Class and Preferred Term	Open-label losmapimod (Pre-COVID-19) Analysis Set	R	9.1.5	Safety		
Table	14.3.1.6	Treatment-Emergent Adverse Events Leading to Study Withdrawal by System Organ Class and Preferred Term	Safety Analysis Set	R	9.1.6	Safety		
Table	14.3.1.6.1	Treatment-Emergent Adverse Events Leading to Study Withdrawal by System Organ Class and Preferred Term	Open-label losmapimod (Pre-COVID-19) Analysis Set	R	9.1.6	Safety		
Table	14.3.2.1	Serious Treatment-Emergent Adverse Events by System Organ Class and Preferred Term	Safety Analysis Set	R	9.1.4	Safety		

TLF	Table Number	Title	Analysis Set	Unique (U)/Repeat (R)	Section	Efficacy/Safety/Standard	Topline	IA
Table	14.3.2.1.1	Serious Treatment-Emergent Adverse Events by System Organ Class and Preferred Term	Open-label losmapimod (Pre-COVID-19) Analysis Set	R	9.1.4	Safety		
Table	14.3.2.2	Adverse Events Leading to Death by System Organ Class and Preferred Term	Safety Analysis Set	R	9.1.7	Safety		
Table	14.3.2.2.1	Adverse Events Leading to Death by System Organ Class and Preferred Term	Open-label losmapimod (Pre-COVID-19) Analysis Set	R	9.1.7	Safety		
Table	14.3.4.1.1	Change from Baseline in Hematology	Safety Analysis Set	U	9.2.1	Safety		
Table	14.3.4.1.1.1	Change from Baseline in Hematology	Open-label losmapimod (Pre-COVID-19) Analysis Set	R	9.2.1	Safety		
Table	14.3.4.1.2	Shift from Baseline in Hematology	Safety Analysis Set	U	9.2.1	Safety		
Table	14.3.4.1.2.1	Shift from Baseline in Hematology	Open-label losmapimod (Pre-COVID-19) Analysis Set	R	9.2.1	Safety		
Table	14.3.4.2.1	Change from Baseline in Chemistry	Safety Analysis Set	R	9.2.2	Safety		
Table	14.3.4.2.1.1	Change from Baseline in Chemistry	Open-label losmapimod (Pre-COVID-19) Analysis Set	R	9.2.2	Safety		
Table	14.3.4.2.2	Shift from Baseline in Chemistry	Safety Analysis Set	R	9.2.2	Safety		
Table	14.3.4.2.2.1	Shift from Baseline in Chemistry	Open-label losmapimod (Pre-COVID-19) Analysis Set	R	9.2.2	Safety		
Table	14.3.4.2.3	Summary of Clinically Notable Laboratory Results by Visit - Chemistry (Liver)	Safety Analysis Set	U	9.2.2	Safety		

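### With two wide ECG windows, one value kept in each and no worst post-baseline row, for-cause QTcF outliers can be missing from the QTcF category table

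*SAP*

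**What the plan says.** - **Selection within a window.** SAP 4.5 limits its rule to by-visit output: "For summaries displayed by visit, multiple values for a given assessment within a time window will be handled as follows". For safety data, "The first non-missing value to the nominal timepoint will be assigned to the visit". For efficacy data, by contrast, "The nearest non-missing value to the nominal timepoint will be assigned to the visit".
- **Windows.** SAP 4.4 states "Visit windows will be continuous from the midpoint between two consecutive study visits", separately for each variable according to its own schedule. Table 4-1 gives vital signs as the worked example.
- **What is mapped.** SAP 4.4: "Data mapped to scheduled visits will include all data collected up to the reporting cut-off date and may include withdrawal visits and unscheduled visits". The wording on withdrawal and unscheduled visits is permissive.
- **ECG schedule.** Protocol Table 13-1 and SAP 15.7.1 place ECGs at screening, baseline, Week 4, Week 48, early termination (ET) and safety follow-up, with none at Weeks 12, 16, 24 or 36. SAP 9.5 also foresees ECGs when clinically indicated.
- **QTcF output.** SAP 9.5: "A categorical summary of QTcF values and change from baseline at each visit will be presented". The categories run up to above 500 msec, and to an increase of more than 60 msec. Neither SAP 9.5, nor the planned table (14.3.5.3.3), nor the SAP addendum provides a worst post-baseline row. For a different table, the overall ECG evaluation, SAP 9.5 names End of Treatment and Safety Follow-up as rows separate from Week 48.
- **Liver output.** SAP 9.2.2 counts a subject as notable if a criterion is met at any point in the treatment period, and its shift tables use the maximum post-baseline value. The planned Table 14.3.4.2.3 is nevertheless titled "Summary of Clinically Notable Laboratory Results by Visit - Chemistry (Liver").

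**The concern.** An outlier table exists to show whether any subject crossed a threshold. Here the scheduled on-treatment ECGs are 44 weeks apart, so an ECG prompted by symptoms or by concern about the QT interval falls inside one of two very wide windows and competes with a routine ECG for a single slot. With no any-time row, a threshold crossing between visits can be missing from the one table designed to count it.

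The QT interval is a live question for this drug. Protocol 1.4 reports that in a thorough QT study the upper 90% confidence bound for the placebo-corrected QTcF change at 7.5 mg BID "exceeded the 10 msec threshold at multiple time points", and that it also crossed the threshold at 20 mg daily at the 24-hour point. The same section reports no QTcF above 480 msec, no increase of 60 msec or more, and modelling at about twice the 15 mg BID exposure in which the bound stayed within 10 msec. That mixed record is a reason to count outliers completely; it does not show that there will be any.

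**Working it through.** **Inputs.** Nominal days 28, 84, 112, 168, 252 and 336 (SAP Table 4-1). The first extension visit is Week 60, that is 60 × 7 = Day 420 (Protocol Table 13-2). The scheduling tolerance is ±5 days at Weeks 4 and 48 (Protocol Table 13-1).

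**Step 1: reproduce Table 4-1.** The upper limit of each window is the midpoint of two consecutive scheduled days:
- (28 + 84)/2 = 56
- (84 + 112)/2 = 98
- (112 + 168)/2 = 140
- (168 + 252)/2 = 210
- (252 + 336)/2 = 294
- (336 + 420)/2 = 378

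The SAP gives 56, 98, 154, 210, 294 and 378. Five of six agree. The sixth, 154 against 140, is the Week 16 extension that SAP 4.4 announces. The midpoint rule is therefore read correctly.

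**Step 2: apply it to ECGs (Days 28, 336, 420).** (28 + 336)/2 = 182 and (336 + 420)/2 = 378. The Week 4 window is Days 2-182; the Week 48 window is Days 183-378.

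**Step 3: days affected.**
- A Week 4 ECG done on schedule falls no later than Day 28 + 5 = 33. A later ECG in the same window, Days 34-182, is not selected: 182 − 33 = 149 days, 149/336 = 44% of the 48 weeks.
- A Week 48 ECG done on schedule falls no earlier than Day 336 − 5 = 331. An unscheduled ECG on Days 183-330 comes before it: 330 − 182 = 148 days, 148/336 = 44%. It takes the Week 48 slot only if 'first' means earliest in the window.

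**Step 4: test the rules on examples.** The QTcF values (msec) are assumptions chosen for illustration; the documents give none.

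| ECGs (day: value) | Earliest in window: Week 4 / Week 48 | Nearest to nominal day: Week 4 / Week 48 | Any-time worst |
|---|---|---|---|
| (a) 28: 430; 100 for-cause: 505; 336: 432 | 430 / 432 | 430 / 432 | 505 |
| (b) 28: 430; 200 for-cause: 432; 336: 505 | 430 / 432 | 430 / 505 | 505 |
| (c) 28: 430; 200 for-cause: 505; 336: 432 | 430 / 505 | 430 / 432 | 505 |

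In (a) the outlier is lost under both readings. In (b) the earliest-value rule loses the true Week 48 outlier. In (c) the earliest-value rule keeps the outlier, labelled Week 48, while the nearest-value rule loses it. Only the any-time row keeps it in all three. If unscheduled ECGs are not mapped at all, the for-cause values in (a) and (c) are likewise absent.

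**The case against.** Several stronger readings are tempting, and the documents do not support them.

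- **That an ET ECG replaces the Week 48 ECG.** It cannot. The ET visit is for subjects leaving the study, who have no later Week 48 ECG. At most, an ET ECG mapped by day is hidden behind Week 4 (up to Day 182) or labelled Week 48 (after it). It may also have its own row: SAP 9.5 names End of Treatment for the neighbouring evaluation table. The SAP does not say whether the QTcF table follows that list, or whether End of Treatment means the ET visit.
- **That Week 48 is certainly displaced.** This needs unscheduled data to be mapped, which SAP 4.4 only permits, and needs 'first' to mean earliest. The SAP 4.5 phrase is garbled and may have been meant as nearest. Week 48 would then be protected, but case (a) would still be lost.
- **That outliers survive only in a listing.** SAP 4.1 does list all repeat and unscheduled assessments, but Protocol 6.2.6 also makes clinically significant ECG changes reportable as adverse events, so those reach the adverse event tables.
- **That counts are biased downward overall.** Not shown. After Day 182, the earliest-value rule can keep a for-cause outlier (c) or lose a scheduled one (b), and no document gives the number of for-cause ECGs.
- **That liver peaks are lost.** SAP 9.2.2 has the any-time definition and maximum-value shift tables. Potential drug-induced liver injury is also an event of special interest with a dedicated listing. What stands is that the title of Table 14.3.4.2.3 does not match that definition.

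These points narrow the concern. They do not supply an any-time QTcF count.

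**Conclusion.** The concern holds in a limited form. Under each reading of SAP 4.4 and 4.5, a for-cause QTcF outlier on about Days 34-182 is missing from the category table, given that a Week 4 ECG was done. If unscheduled ECGs are mapped and 'first' means earliest, a for-cause ECG on about Days 183-330 also takes the place of the actual Week 48 ECG. If they are not mapped, for-cause ECGs are absent from the table throughout. Each of the two periods is about 44% of the 48 weeks. This measures exposure to the problem; it does not estimate how many outliers would be missed.

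The consequence is an incomplete descriptive safety table. Individual ECGs remain in the listings and efficacy conclusions are untouched. It should still be corrected before the tables are programmed, because the SAP already uses any-time or maximum-value logic for laboratory data and the present wording allows two programmers to produce different counts.

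**What to change.** 1. In SAP 9.5 and Table 14.3.5.3.3, add a row for the worst post-baseline on-treatment QTcF, both absolute category and change from baseline, using all scheduled, unscheduled and ET ECGs.
2. Add the matching row for any time during treatment to Table 14.3.4.2.3, so that it agrees with SAP 9.2.2.
3. State that ET and Safety Follow-up ECGs have their own rows in the QTcF table.
4. Reword the SAP 4.5 safety rule so that by-visit rows use the scheduled-visit value, or the value nearest the nominal day. This protects Week 48 but does not replace item 1, as cases (a) and (c) show.

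The cost is SAP wording and one extra summary row in each of two existing tables, with no new data collection. Outlier counts may come out slightly higher.

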4.6. Subgroup

A subgroup analysis will be performed for the following subsets at baseline:

- 1) Repeat category (1 to 3 repeats, 4 to 9 repeats)
- 2) Clinical severity score (RICCI score 2 to 3, 3.5 to 4)

- 3) Sex (Male, Female)
- 4) Fat Fraction at biopsy site. This is an average of results from 2 Readers.
 - a. > 10 to <=20%
 - b. >20 to <=40%
- 5) Mean DUX4 score (DUX4 Score 1) at baseline values partitioned by 3 thresholds:
 - a. >=Q1 (first quartile of observed mean DUX4 score (DUX4 Score 1) at baseline)
 - b. >=Q2 (median of observed mean DUX4 score (DXU4 Score 1) at baseline)
 - c. >=Q3 (third quartile of observed mean DUX4 score (DXU4 Score 1) at baseline)
- 6) Subjects completing 'RWS protocol with above shoulder movements' at baseline
- 7) Subjects who completed 'RWS protocol with above shoulder movements' all through the study
- 8) Subjects completing the classical TUG, without an assisted device, at baseline
- 9) Subjects completing the FSHD TUG, without an assisted device, at baseline
- 10) MFF_{tot}, LMV_{tot} and MFI_{tot} with thresholds at the median of observed baseline data
- 11) Subjects with non-censored laboratory observations for DUX4 score at baseline.

Endpoints for which the subgroup analysis will be performed are indicated in subsequent sections.

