The quantification of gene expression and normalization of qPCR are conducted at a central laboratory (Q2 Lab Solutions) in a blinded fashion, with no access to treatment assignment information. A total of six DUX4-regulated gene transcripts (CCNA1; KHDC1L; MBD3L2; PRAMEF6; SLC34A2; ZSCAN4) have been pre-selected for inclusion in the mean DUX4 score. DUX4 Score 1 will be used for the primary analysis. A second and third composite scores (DUX4 Score 2 and DUX4 Score 3, respectively) will be used for sensitivity analysis. For details on assay validation, gene subset selection criteria/process, and derivation of DUX4 Score, see [Appendices 15.1 – 15.5](#).

DUX4 score 1 will be summarized as change from baseline to either Week 16 or Week 36. Study subjects can only have one post-baseline biopsy (either Week 16 or Week 36, but not both). If the pre-treatment or on-treatment DUX-4 results are unavailable, then the assessment is considered missing. See [Section 8.2.1](#) for details of missing data handling for DUX4 Score.

For each treatment, descriptive statistics of aberrant DUX4 activity will be presented at Baseline and post-baseline (Week 16 or Week 36) as well as change from baseline. An ANCOVA model

will be used to analyze the change from baseline in DUX4 activity in affected skeletal muscle, which is the response variable, with repeat number category and treatment group as fixed effects and baseline DUX4 activity in affected skeletal muscle as a covariate. Within-group least-squares (LS) means, the associated standard errors (SEs) and 2-sided 95% CIs, treatment differences in LS means and the associated 2-sided 95% CIs and 2-sided p-values will be derived from the model and presented in the table. If the model-based p-value of the treatment difference in the change from baseline is less than the final alpha provided in [Table 12-1](#), the difference between two treatment groups will be determined to be statistically significant.

Similar methods will be used to analyze the change from baseline in DUX4 activity within subgroups identified in [Section 4.6](#) to evaluate consistency of treatment effects across the subgroups. For the repeat category subgroup analysis, the repeat category will be excluded as fixed effect from the model.

The LS mean change from baseline by visit of the DUX4 activity will be graphically presented.

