8.4. Clinical Outcome Assessments

8.4.1. Reachable Work Space With and Without Weights

The reachable work space (RWS) is a 3-dimensional sensor-based system (using a single depth-ranging sensor) that can unobtrusively detect an individual's RWS and reflects an individual global upper extremity function, including shoulder and proximal arm. The evaluation will be performed with and without weights and on both the right and left arms at Baseline, Week 4, Week 12, Week 24, Week 36, Week 48 and Safety Follow-up.

The absolute total RWS surface envelope area (m^2) as well as areas for each of the quadrants will be calculated and provided by a vendor in a blinded fashion, with no access to treatment assignment information. The reachable workspace relative surface area (RSA) represents the portion of the unit hemisphere that is covered by an individual's hand movement.

For each treatment, descriptive statistics of RSA results per visit as well as the change from baseline will be presented by quadrant, for total upper quadrants (Q1+Q3) and total area (Q1+Q2+Q3+Q4) for the assessment with weights and without weights, and by dominant and non-dominant arm. An MMRM model will be used to analyze the change from baseline in total area with repeat number category, treatment group, visit, and treatment-by-visit interactions as fixed effects and baseline value of the total area as a covariate. A separate model will be run with and without weights and for the dominant and non-dominant hand. Within-group LS mean changes from baseline, the associated SEs and 2-sided 95% CIs, treatment differences in LS mean changes from baseline at post-baseline visits and the associated 2-sided 95% CIs and 2-sided p-values will be derived from the MMRM model and will be provided in the summary table. An unstructured covariance matrix will be used to model the correlation among repeated measurements within each subject. If models using unstructured covariance do not converge, an AR(1) covariance structured will be used instead. Similar methods will be used to analyze the change from baseline in RSA for each quadrant.

Summary tables will be generated, showing percentage of subjects with RWS decline of $\geq 5\%$, $\geq 2\%$ at each post-baseline timepoint.

See [Section 4.6, #6](#) and [#7](#), for sub-group analyses to be conducted on this endpoint.

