3.2. Subgroup

For the subgroup analysis, RWS will be presented according to protocol type instead of just presenting subjects who have above shoulder movements.

1. Protocol Type (High or Low - for Subjects Who Completed RWS Protocol With Above Shoulder Movements or Below Shoulder Movements at Baseline).
2. Protocol Type (High or Low - for Subjects Who Completed RWS Protocol With Above Shoulder Movements or Below Shoulder Movements All Through the Study).

Subgroup no. 8, subjects completing the classical TUG, without an assisted device at baseline, will be updated to also consider subjects with assisted device at baseline. Hence, the subgroup presentation will be based according to use or non-use of assisted device at baseline for subjects who completed the classical TUG.

In the same manner, subgroup no. 9, subjects completing the FSHD TUG, without an assisted device, at baseline, will be updated to consider subjects with assisted device at baseline. Hence, the subgroup presentation will be based according to use or non-use of assisted device at baseline for subjects who completed the FSHD TUG.

Subgroup no. 10, MFF_{tot}, LMV_{tot} and MFI_{tot} with thresholds at the median of observed baseline data, will be based on the Longitudinal Reference Value at Screening.

4. Treatment Compliance

Additional categories for compliance will be included and the existing categories will be updated as follows:

- <40%
- 40-<60%
- 60-<80%
- 80-<120%
- >120%

5. Efficacy Analysis

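### One SAP subgroup is defined by arm performance after randomisation, and the baseline DUX4 bands are nested with no band below the first quartile

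*SAP*

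**What the plan says.** SAP 4.6 opens its list of eleven subgroups with "A subgroup analysis will be performed for the following subsets at baseline". Two entries concern the Reachable Work Space (RWS) test:

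- Item 6: "Subjects completing 'RWS protocol with above shoulder movements' at baseline".
- Item 7: "Subjects who completed 'RWS protocol with above shoulder movements' all through the study".

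SAP 8.4.1 schedules RWS at "Baseline, Week 4, Week 12, Week 24, Week 36, Week 48 and Safety Follow-up". Addendum 3.2 re-presents both items as High or Low protocol type. Its second entry is still defined by "Above Shoulder Movements or Below Shoulder Movements All Through the Study".

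Item 5 of SAP 4.6 reads "Mean DUX4 score (DUX4 Score 1) at baseline values partitioned by 3 thresholds". The first band is ">=Q1 (first quartile of observed mean DUX4 score (DUX4 Score 1) at baseline"; the other two are at or above the median and at or above the third quartile. The addendum does not alter them.

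For DUX4, SAP 8.2 applies the SAP 4.6 subgroups "to evaluate consistency of treatment effects across the subgroups", and SAP 8.3 gives the same purpose for the MRI composites. In SAP 15.8, item 7 feeds:

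- DUX4, marked for topline (Table 14.2.2.1.8)
- the MFF, LMV and MFI composites (Tables 14.2.3.1.1.8, 14.2.3.2.1.8 and 14.2.3.3.1.8)
- RWS itself (Table 14.2.4.1.1.3)

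SAP section 12 lists subgroups 1 to 5 and 11 for the interim presentation to the sponsor. Item 5 is therefore shown there and item 7 is not.

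**The concern.** A subgroup preserves the randomised comparison when membership is fixed before treatment can act. Item 7 membership runs through Week 48 and the safety follow-up, and it rests on an arm-function test that is itself an efficacy outcome. If losmapimod helps weaker subjects stay in the above-shoulder category, the losmapimod members include weaker people than the placebo members, and the two are no longer comparable. Three features of this trial add to the difficulty:

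- The post-baseline biopsy is at Week 16 or Week 36, so membership for the DUX4 comparison can depend on later visits.
- For the 12 subjects who rolled over at Week 24, later visits take place on open-label losmapimod whatever their randomised arm.
- Protocol 3.2.2 reports missed visits, and no rule says whether a missed RWS visit breaks membership.

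Item 5 raises a different issue. Its bands are fixed at baseline, but each sits inside the previous one and the lowest quarter is in none. Similar results across the bands could be read as consistency when much of the similarity comes from shared subjects. This display also goes to the sponsor at the interim, with p-values.

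**Working it through.** **Sample size, reproduced first.** SAP 4.7 gives effect size 0.70, two-sided 0.05, 80% power, 68 evaluable and 76 randomised. The exact t-test calculation needs 33.02 per arm, rounded up to 34 (68 in total; power 81.2%). Then 68 / 0.90 = 75.6, rounded up to 76. Both figures reproduce, and 68 sets the band sizes below.

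**Item 7: illustrative bias.** The documents give no retention rate and no RWS effect, so these inputs are assumptions:

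- RWS change has SD 1, and higher is better.
- A subject stays in the group when the change exceeds a cut-off c, so RWS change fully determines selection.
- The true effect is d = 0.5 SD.

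If a fraction p of placebo is retained, c = Φ⁻¹(1 − p). With h(x) = φ(x)/[1 − Φ(x)], the retained means are h(c) on placebo and d + h(c − d) on losmapimod. Losmapimod retention is 1 − Φ(c − d).

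| Placebo retained | Losmapimod retained | Placebo mean | Losmapimod mean | Difference | Attenuation |
|---|---|---|---|---|---|
| 95% | 98% | 0.109 | 0.541 | 0.43 | 14% |
| 90% | 96% | 0.195 | 0.585 | 0.39 | 22% |
| 80% | 91% | 0.350 | 0.678 | 0.33 | 34% |
| 60% | 77% | 0.644 | 0.888 | 0.24 | 51% |

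For another outcome with no true effect, correlated 0.5 with RWS change, the spurious difference is 0.5 × [h(c − d) − h(c)]. That gives −0.03, −0.06, −0.09 and −0.13 SD in the same row order. If treatment does not shift RWS change (d = 0), the two h terms are equal and the bias is zero.

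**Item 5: overlap.** With 68 evaluable, the bands hold 0.75 × 68 = 51, 0.50 × 68 = 34 and 0.25 × 68 = 17 subjects. For nested sets with equal variance, the correlation of the two effect estimates is √(n small / n large):

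- first-quartile and median bands: √(34/51) = 0.82
- median and third-quartile bands: √(17/34) = 0.71
- first- and third-quartile bands: √(17/51) = 0.58

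Simulation of 10,000 trials of 68 subjects gave 0.81, 0.69 and 0.57. Estimates from disjoint quartile bands were essentially uncorrelated (absolute value at most 0.012).

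**Item 5: what the bands reveal.** True effects by baseline quarter, lowest to highest:

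| Effect by quarter | Three planned bands | All subjects |
|---|---|---|
| 0, 0.70, 0.70, 0.70 | 0.70, 0.70, 0.70 | 0.75 × 0.70 = 0.53 |
| −0.70, 0.70, 0.70, 0.70 | 0.70, 0.70, 0.70 | 0.525 − 0.175 = 0.35 |
| 0, 0, 0, 0.70 | 0.23, 0.35, 0.70 | 0.25 × 0.70 = 0.18 |

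In the first two rows no planned band shows that the lowest quarter differs. In the third row the bands do show a gradient.

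**The case against.** Several points on the other side stand.

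- **Nested bands are not invalid.** A reader might infer that they cannot show whether the effect varies with baseline DUX4. That goes too far: each band is a randomised comparison, and an effect confined to the top quarter appears as a gradient. Cumulative thresholds are also a recognisable enrichment display. Subjects below the first quartile still contribute to the full analysis set result, so a different effect there is diluted in that result, though absent from every band.
- **The item 7 bias is conditional.** A reader might infer that every item 7 estimate is biased. It is not if treatment leaves membership unchanged. Protocol 1.1 puts strength loss at 1% to 4% a year, so loss of above-shoulder movement within 48 weeks may be uncommon, which favours the upper rows of the retention table. In this model the bias runs against losmapimod and does not create an apparent benefit.
- **The addendum changed something.** It supplies the Low group. How the protocol type is assigned, and whether it is decided again at each visit, is not stated; Protocol 6.4.1 defers operational detail to an RWS manual. Restricting to one test version could serve comparability of change scores. Membership is nevertheless still settled after randomisation, and as worded a subject who moves between versions belongs to neither group.
- **Disjoint quartiles are small.** A band of 17 has about 27% power at effect size 0.70.
- **The consequence is limited.** No subgroup enters the testing hierarchy, RWS is exploratory, and item 7 is not among the interim outputs.

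**Conclusion.** Item 7 and its addendum counterpart are not baseline subsets, and treatment comparisons within them should not be read as randomised evidence of consistency. The possible bias is unknown in size. The 14% to 51% attenuation shown rests on assumed retention of 95% down to 60%, an assumed 0.5 SD effect and selection determined wholly by RWS change; with no treatment effect on membership it is zero.

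For item 5 the defects are narrower: the label does not match nested bands, the lowest quarter has no band, and agreement between neighbouring bands is weak evidence because their estimates correlate at about 0.82 and 0.71 through overlap alone (equal variance assumed). A reader might go on to doubt the main result. The documents do not support that: the primary full-analysis-set test and the three-endpoint hierarchy in SAP 8.1 use neither subgroup. The point is worth correcting because item 7 reaches a topline DUX4 table and item 5 reaches the interim presentation.

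**What to change.** **Item 7.** Remove it, and the second entry of addendum 3.2, as treatment-comparison subgroups. Rely on the baseline version, item 6, which SAP 15.8 already plans for DUX4 (Table 14.2.2.1.7), the three MRI composites (Tables 14.2.3.1.1.7, 14.2.3.2.1.7 and 14.2.3.3.1.7) and RWS (Table 14.2.4.1.1.2). If keeping above-shoulder movement is of interest, report the proportion doing so at each visit by randomised arm, as an outcome.

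**Item 5.** Either keep the cumulative bands, stop calling them a partition and add the group below the first quartile, or use disjoint bands, for example below and at or above the median. In both cases add a treatment-by-baseline-DUX4 interaction estimate with its confidence interval, and label the set descriptive.

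**Cost.** SAP wording, a few tables fewer and a few re-specified; no new data. The downside is wide intervals: about 17 evaluable subjects per quartile band, or 34 per half with a median split.
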